7.10.1.2. Dispensing of INCB050465

An initial bulk supply of INCB050465 tablets will be provided to investigative sites before enrollment of the first subject. Thereafter, the site staff will contact the sponsor for resupply of INCB050465. When dispensing to subjects, the investigator or designee will remove the appropriate quantity of INCB050465 from their stock, dispense the medication, and enter the amount dispensed into the eCRF and drug accountability log. Full details will be provided in the Pharmacy Manual.

7.10.1.3. Assessment of Compliance With INCB050465

The study subject will return to the clinic with full, empty, and partially full bottles of INCB050465 tablets at the beginning of each treatment cycle or at routine visits or every 12 weeks or as defined by standard of care, and a compliance check (tablet count) will be performed by the clinic staff. Appropriate steps should be taken to optimize compliance.

7.10.1.4. Administration of INCB039110

Subjects will self-administer INCB039110 orally, with water, according to a QD regimen as directed by the investigator. INCB039110 should be taken on an empty stomach if possible

(refrain from food consumption during the period 2 hours before and 1 hour after INCB039110 administration) and can be administered at the same time as INCB050465. INCB039110 should be administered in the morning.

INCB039110 will be administered in the study clinic as indicated in [Table 5](#); subjects will attend the study visit having fasted, recorded the time of the prior administration of INCB039110 and prior meal, and having withheld the morning dose of INCB039110. At this visit, PK [REDACTED] sampling will be conducted. INCB039110 dose administration will be started on Cycle 1 Day 1 after INCB050465 PK sampling is complete.

7.10.1.5. Dispensation of INCB039110

For subjects enrolled in either Part 2 or Part 3 Expansion Cohort E, an initial bulk of INCB039110 will be provided to investigative sites prior to enrollment of the first subject. Thereafter, the site staff will contact the sponsor for resupply of INCB039110. When dispensing to subjects, the investigator or designee will remove the appropriate quantity of INCB039110 from their stock, dispense the medication, and enter the amount dispensed into the CRF and drug accountability log. Full details will be provided in the Study Manual.

7.10.1.6. Assessment of Compliance With INCB039110

For subjects enrolled in either Part 2 or Part 3 Expansion Cohort E the study subject will return to the clinic with full, empty, and opened/partially used bottles of INCB039110 at the beginning of each treatment cycle or at routine visits or every 12 weeks or as defined by standard of care, and a compliance check (tablet count) will be performed by the clinic staff. Appropriate steps should be taken to optimize compliance.

7.10.1.7. Sourcing and Administration of Standard of Care Agents

The standard of care agents described above will be supplied by the site. These agents are all administered by intravenous infusion in clinic.

7.10.1.8. Assessment of Compliance With Standard of Care Agents

The site will document the amount of infusion administered to the subject at each appropriate visit. This information will be captured in the eCRF.

7.10.1.9. Administration of Supportive Care

Supportive care, including GCSF for treatment of chemotherapy-induced neutropenia, will be supplied by the institution's pharmacy and administered according to the package insert and institutional guidelines.

7.10.2. Distribution of Subject Reminder Cards/Subject Diaries

Subjects will be provided with subject reminder cards at each visit. The subject reminder cards will indicate the date and time of the next visit. Reminder cards will include instructions specific for Day 8 and Day 15 study visits, at which time the subject will refrain from taking the study drug at home in the morning before the clinic visit. All necessary instructions, such as administration instructions for study drug, concomitant medications, and reminders of visits to conduct laboratory tests, should be provided to the subject in writing on this reminder card, or on

accompanying written materials. Subject diaries will be provided for the purpose of documenting study drug administration and AEs. The subject diary will have an area on which the date and time of the last dose taken before each visit will be recorded as well as the time (and content if applicable to the visit) of the last meal.

After implementation of Amendment 10, subjects will receive reminder cards that will include the date and time of the next visit and instructions for study treatment administration.

8. SAFETY MONITORING AND REPORTING

8.1. Adverse Events

8.1.1. Definitions and Reporting

For the purposes of this Protocol, an AE is defined as the appearance of (or worsening of any pre-existing) undesirable sign(s), symptom(s), or medical condition(s) that occur after a subject provides informed consent. Abnormal laboratory values or test results occurring after informed consent constitute AEs only if they induce clinical signs or symptoms, are considered clinically meaningful, require therapy (eg, hematologic abnormality that requires transfusion), or require changes in the study drug(s).

Adverse events that begin or worsen after informed consent should be recorded on the Adverse Events page of the CRF. Conditions that were already present at the time of informed consent should be recorded on the Medical History page of the CRF. Adverse event monitoring should be continued for at least 30 days after the last dose of study drug. Adverse events (including laboratory abnormalities that constitute AEs) should be described using a diagnosis whenever possible rather than by individual underlying signs and symptoms. When a clear diagnosis cannot be identified, each sign or symptom should be reported as a separate AE.

Adverse events will be assessed according to the CTCAE version 4.03. The CTCAE severity Grade 5 (death) will not be used in this study; rather, information about deaths will be collected as an outcome of the event. The occurrence of AEs should be sought by nondirective questioning of the subject during the screening process after signing the ICF and at each visit during the study. Adverse events may also be detected when they are volunteered by the subject during the screening process or between visits, or through physical examination, laboratory test, or other assessments.

As far as possible, each AE should be evaluated to determine:

- The severity grade (CTCAE Grade 1 to 4).
- Reasonable possibility that the AE is related to the study treatment: unrelated (no) or related (yes).
 - **NOTE: for subjects receiving combination therapy, causality assessment for each agent administered per study must be indicated.**
- Start and end dates, unless unresolved at final examination.
- Action taken with respect to study drug (eg, none, dose adjusted, temporarily interrupted, permanently discontinued, unknown, not applicable).

- Outcome (eg, not recovered/not resolved, recovered/resolved, recovering/resolving, recovered/resolved with sequelae, fatal, unknown).
- Whether it is serious, as per serious adverse event (SAE) definition provided in Section 8.3.1.

Unlike routine safety assessments, SAEs are monitored continuously and have special reporting requirements, see Section 8.3.2.

All AEs should be treated appropriately. If a concomitant medication or nondrug therapy is given, this action should be recorded on the AE and Prior/Concomitant medications pages of the CRF.

Once an AE is detected, it should be followed until it has resolved or until it is judged to be permanent; assessment should be made at each visit (or more frequently if necessary) of any changes in severity, the suspected relationship to the study drug, the interventions required to treat it, and the outcome.

Disease progression should not be regarded or reported as an AE itself, unless it is associated with a separate AE.

Upon implementation of Amendment 10, AEs leading to treatment discontinuation and all SAEs regardless of causal relationship must be reported on the AE CRF.

8.2. Laboratory Test Abnormalities

8.2.1. Definitions and Reporting

Laboratory abnormalities that constitute an AE in their own right (are considered clinically meaningful, induce clinical signs or symptoms, require concomitant therapy, or require changes in study drug), should be recorded on the AE page of the CRF. Whenever possible, a diagnosis rather than a symptom should be provided (eg, anemia instead of low hemoglobin). Laboratory abnormalities that meet the criteria for AEs should be followed until they have returned to normal or an adequate explanation of the abnormality is found. When an abnormal laboratory test result corresponds to a sign or symptom of a previously reported AE, it is not necessary to separately record the laboratory test result as an additional event.

Laboratory abnormalities that do not meet the definition of an AE should not be reported as AEs. A Grade 3 or 4 (severe) AE, as per CTCAE, does not automatically indicate an SAE unless it meets the definition of serious, as defined in Section 8.3.1, and/or per the investigator's discretion. A dose interruption or adjustment for the laboratory abnormality may be required (see Section 5.6) and should not contribute to the designation of a laboratory test abnormality as an SAE.

8.3. Serious Adverse Events

8.3.1. Definitions

A SAE is defined as an event that meets 1 of the following criteria:

- Is fatal or life-threatening (ie, immediate risk of dying).
- Results in persistent or significant disability or incapacity.
- Constitutes a congenital anomaly or birth defect.
- Is clinically meaningful (ie, defined as an event that jeopardizes the subject or requires potential medical or surgical intervention to prevent 1 of the outcomes listed above). Considered meaningful by the investigator as an important medical event that may not result in death, be life-threatening, or require hospitalization, but may be considered a SAE when, based upon appropriate medical judgment, it may jeopardize the subject or may require medical or surgical intervention to prevent 1 of the outcomes listed in this definition.
- Requires inpatient hospitalization or prolongation of existing hospitalization, unless hospitalization is a result of:
 - Routine treatment or monitoring of the studied indication not associated with any deterioration in condition
 - Elective or preplanned treatment for a pre-existing condition that is unrelated to the indication under study and has not worsened since signing the ICF.
 - Treatment on an emergency outpatient basis for an event not fulfilling any of the definitions of a SAE given above and not resulting in hospital admission.
 - Social reasons and respite care, in the absence of any deterioration in the subject's general condition.
 - Any SAEs that are expected due to the condition being treated, including if the SAE is a primary outcome measure, or where there has been a clear agreement with regulators not to consider these as SAEs, provided the information is collected elsewhere.

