4.3.1. Primary Endpoint

- Safety and tolerability of the planned study treatments as assessed by summary of AEs, clinical laboratory assessments, physical examination results, and 12-lead ECGs.

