7.4.1. Adverse Events

Adverse events will be monitored from the time the subject signs informed consent. Subjects will be instructed to report all AEs during the study and subjects will be assessed for the occurrence of AEs throughout the study. In order to avoid bias in eliciting AEs, subjects will be asked general, nonleading questions such as "How are you feeling?" All AEs (serious and nonserious) must be recorded on the source documents and CRFs regardless of the assumption of a causal relationship with the study drug. The definition, reporting, and recording requirements for AEs are described in Section 8.

Upon implementation of Amendment 10, AEs that lead to the discontinuation of study treatment and all SAEs must be recorded in the CRFs, regardless of the assumption of a causal relationship with the study drug(s).

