8.3.2. Reporting

To ensure subject safety, every SAE, regardless of suspected causality, occurring after the subject has signed the ICF and up to the last study visit, or up to 30 days after the subject has stopped study treatment, whichever is later, must be reported to the sponsor (or designee) within 24 hours of learning of its occurrence. Any SAEs experienced after this period should be reported to the sponsor (or designee) only if the investigator suspects a causal relationship to the study drug. Recurrent episodes, complications, or progression of the initial SAE must be reported as the follow-up to the original episode within 24 hours of the investigator receiving the follow-up information. An SAE occurring at a different time interval or otherwise considered completely unrelated to a previously reported one should be reported separately as a new event.

Previously planned (before providing informed consent) surgeries should not be reported as SAEs unless the underlying medical condition worsens over the course of the study.

Information about all SAEs is collected and recorded on the Serious Adverse Event Report Form. The investigator must assess and record the relationship of each SAE to each specific study drug (if there is more than 1), complete the SAE Report Form in English, and send the completed, signed form by fax within 24 hours to the sponsor or its designee. The investigator must assess if there is a reasonable possibility that the SAE is related to the study treatment: unrelated (no) or related (yes).

Serious AEs related to unblinded comparator drugs or concomitant medications/drug delivery systems are reported directly to the manufacturers of those drugs/devices in accordance with the package insert.

The telephone and facsimile number of the sponsor's contact persons, specific to the study, are listed in the investigator folder provided to each site. The original copy of the SAE Report Form and the fax confirmation sheet must be kept with the CRF documentation at the study site.

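### The hospitalisation exemption in the SAE definition (Protocol 8.3.1) does not suit a trial with a safety primary endpoint: disease-like drug toxicities can lose SAE status and, after Amendment 10, may go unrecorded

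*Protocol*

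**What the plan says.** Protocol Section 8.3.1 lists the criteria that make an event serious. The hospitalisation criterion reads "Requires inpatient hospitalization or prolongation of existing hospitalization, unless hospitalization is a result of", and five exceptions follow. The fifth has two limbs. The first is "Any SAEs that are expected due to the condition being treated, including if the SAE is a primary outcome measure". The second covers events that regulators have clearly agreed not to treat as SAEs. The bullet closes with the condition "provided the information is collected elsewhere", which I read as governing both limbs. No other seriousness criterion carries this exception.

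Section 4.3.1 gives the primary endpoint: "Safety and tolerability of the planned study treatments as assessed by summary of AEs, clinical laboratory assessments, physical examination results, and 12-lead ECGs".

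On recording, Section 7.4.1 says "All AEs (serious and nonserious) must be recorded on the source documents and CRFs". Once Amendment 10 is implemented, the same section narrows this to "AEs that lead to the discontinuation of study treatment and all SAEs must be recorded in the CRFs"; Table 9 and Section 8.1.1 agree. Section 8.3.2 requires a report to the sponsor within 24 hours for "every SAE, regardless of suspected causality, occurring after the subject has signed the ICF". SAE counts are tabulated under Protocol Section 9.4.3.1 and SAP Section 8.2.3.

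**The concern.** An exemption for disease-expected or primary-outcome events makes sense where the primary outcome is a disease event that is captured and analysed on its own form. Here the primary outcome is the safety profile. The documents give no list of events expected from the disease, describe no regulator agreement, and do not say where exempted events are collected.

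Each site therefore has to decide whether a hospitalised event is due to the lymphoma before deciding whether it is an SAE. For toxicities that resemble the disease, that decision can take an event out of expedited reporting and out of the SAE tables. The trial has no Data Monitoring Committee (Section 8.7), so the sponsor's safety review depends on what sites report.

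**Working it through.** The clause rests on wording, so the main check sets the sections side by side.

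1. **Which events can the exemption reach?** An event must be serious only through hospitalisation, and must be judged expected from the disease.
   - Section 8.8 names infections and fever as possible consequences of the drug's lymphoid depletion.
   - Section 1.4.4 names infections, and effects on white cell, red cell and platelet counts, as risks of the combination.
   - The disease offers a competing explanation for some of these. Section 5.6.2 notes severe marrow infiltration at entry, and the SAP's Table 1.3.1 shell collects fever as a B-symptom.
   - A site could therefore class an admission for fever or cytopenia as disease-expected in good faith. For infection the documents give less direct support, since they present it as a drug risk.

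2. **Before Amendment 10.** All AEs go on the CRF (Section 7.4.1), so the ordinary AE page can satisfy the collected-elsewhere condition and the exemption can be used. The event stays in the AE and graded TEAE tables. It leaves the 24-hour report and the SUSAR assessment (Section 8.3.2), and the SAE tables.

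3. **After Amendment 10.** Only SAEs and AEs leading to discontinuation are recorded. Laboratory results leave the CRF unless they accompany an SAE (Section 7.4.6), and concomitant-medication data go to the sponsor only for SAEs (Table 9). An exempted event that does not stop treatment has no named place of collection and leaves no indirect trace. Read strictly, the condition then fails and the event remains an SAE. A site that counts its own source notes as elsewhere would reach the opposite answer.

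4. **What is untouched.** Events that are fatal, life-threatening, disabling or important medical events remain SAEs. DLTs rest on type and grade (Section 5.5.1, Table 3), so the 3 + 3 rules and the expansion-cohort stopping rules do not depend on SAE status.

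5. **Illustration of size.** The only related figure in the plan is in Section 9.2: at least a 90% chance that 15 subjects show a toxicity with a true rate of 15%. It reproduces: 1 − 0.85^15 = 0.913. Let f be the share of such cases that lose SAE status. The documents do not give f; it is an assumption. The chance of at least one case being counted as an SAE is 1 − (1 − 0.15(1 − f))^15.

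| Assumed f | Counted rate | Chance of at least one |
|---|---|---|
| 0 | 0.15 | 91.3% |
| 10% | 0.135 | 88.6% |
| 25% | 0.1125 | 83.3% |
| 50% | 0.075 | 68.9% |
| 75% | 0.0375 | 43.6% |

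The chance reaches 90% at a counted rate of 1 − 0.1^(1/15) = 0.1423, that is f = 1 − 0.1423/0.15 = 5.1%. This applies to SAE counts and, after Amendment 10, to recorded events that do not stop treatment. All-AE counts before Amendment 10 stay at 91.3%. Section 9.2 speaks of toxicities, not SAEs, so the plan's own statement is not wrong.

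**The case against.** The strongest defence is that the clause is narrow. It modifies one criterion, requires the event to be expected from the disease, and applies only if the information is collected elsewhere. The primary endpoint summarises AEs, not SAEs alone, so an exempted event was still counted while all AEs were being recorded. All of this stands, and it rules out several stronger readings.

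- A reader might infer that any hospitalised AE is exempt because AEs are the primary outcome. The text does not say so: the primary-outcome phrase is introduced as a case within disease-expected events, not as an alternative to them.
- A reader might infer that Section 8.3.1 contradicts Section 8.3.2. It does not. One section defines an SAE and the other says what to do with it. The effect is that an exempted event never reaches the reporting rule.
- A reader might take the SAEs in Section 1.2.4 (among 46 subjects, colitis and diarrhea in 3 each; pyrexia, pneumonia and dehydration in 2 each) as the number at risk. That section does not say which criterion made them serious. The protocol treats colitis and diarrhea as drug-class toxicities (Section 1.2.3.2, Table 4), not as consequences of lymphoma. That these events were reported as SAEs also shows that such events were being captured.

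What the defence leaves unanswered is that the expected events and the alternative place of collection are undefined, in a trial whose purpose is to characterise toxicity.

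**Conclusion.** The point holds as a weakness in serious-event capture. As written, the clause lets a site withhold SAE status from a hospitalised event that resembles the disease. Before Amendment 10 the loss is limited to expedited reporting and the SAE tables. After Amendment 10 an event that does not stop treatment may also be missing from the database, for subjects still ongoing.

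The documents do not support the inference that primary-endpoint events are removed wholesale, or that dose-escalation decisions are affected. The size cannot be derived from the documents, and the percentages above depend entirely on the assumed f. The conclusion assumes that sites sometimes judge infection, fever or cytopenia to be disease-expected; the documents make this plausible but do not show that it happened.

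**What to change.** In the fifth exception of Section 8.3.1, delete the limb "Any SAEs that are expected due to the condition being treated, including if the SAE is a primary outcome measure". Keep only the regulator-agreement provision, and require that the agreement be documented, the events it covers be listed, and the CRF page that collects them be named. Nothing further is needed for progression: Section 8.1.1 already keeps it out of AE reporting unless a separate AE accompanies it, and the other four exceptions cover routine, elective, emergency outpatient and social care.

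The cost is a protocol amendment, with sponsor and IRB/IEC approval (Sections 11.3 and 13.3), and somewhat more SAE forms. The SAP's SAE tables need no redesign. The deletion works forward only and does not by itself reclassify events already handled under the clause.

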8.3.2. Reporting

To ensure subject safety, every SAE, regardless of suspected causality, occurring after the subject has signed the ICF and up to the last study visit, or up to 30 days after the subject has stopped study treatment, whichever is later, must be reported to the sponsor (or designee) within 24 hours of learning of its occurrence. Any SAEs experienced after this period should be reported to the sponsor (or designee) only if the investigator suspects a causal relationship to the study drug. Recurrent episodes, complications, or progression of the initial SAE must be reported as the follow-up to the original episode within 24 hours of the investigator receiving the follow-up information. An SAE occurring at a different time interval or otherwise considered completely unrelated to a previously reported one should be reported separately as a new event.

Previously planned (before providing informed consent) surgeries should not be reported as SAEs unless the underlying medical condition worsens over the course of the study.

Information about all SAEs is collected and recorded on the Serious Adverse Event Report Form. The investigator must assess and record the relationship of each SAE to each specific study drug (if there is more than 1), complete the SAE Report Form in English, and send the completed, signed form by fax within 24 hours to the sponsor or its designee. The investigator must assess if there is a reasonable possibility that the SAE is related to the study treatment: unrelated (no) or related (yes).

Serious AEs related to unblinded comparator drugs or concomitant medications/drug delivery systems are reported directly to the manufacturers of those drugs/devices in accordance with the package insert.

The telephone and facsimile number of the sponsor's contact persons, specific to the study, are listed in the investigator folder provided to each site. The original copy of the SAE Report Form and the fax confirmation sheet must be kept with the CRF documentation at the study site.

Follow-up information is sent to the same person to whom the original SAE Report Form was sent, using a new SAE Report Form stating that this is a follow-up to the previously reported SAE and giving the date of the original report. Each recurrence, complication, or progression of the original event should be reported as a follow-up to that event regardless of when it occurs. The follow-up information should describe whether the event has resolved or continues, if and how it was treated, and whether the subject continued or withdrew from study participation, or if study drug was interrupted or discontinued.

If the SAE is not previously documented in the IB for the study drug (new occurrence) and is thought to be related to the sponsor's study drug, a sponsor's associate may urgently require further information from the investigator for reporting to health authorities.

The sponsor or its designee may need to issue an Investigator Notification (IN) to inform all investigators involved in any study with the same drug that this SAE has been reported. Suspected Unexpected Serious Adverse Reactions (SUSARs) will be collected and reported to the competent authorities and relevant ethics committees in accordance with Directive 2001/20/EC, or as per national regulatory requirements in participating countries.

Upon implementation of Amendment 10, all SAEs regardless of causal relationship will be reported as described above.

